#### **7.8.5 Duration of response (DOR) & Duration of disease control (DDC)**

DOR can only be determined for patients with OR as defined above.

According to RECIST, the DOR is measured from the time at which the measurement criteria according to RECIST are first met for CR or PR (whichever is first recorded) until the first date that PD is objectively documented according to RECIST (see Section 7.8.6 for details).

- According to iRECIST, the DOR is measured from the time at which the measurement criteria according to iRECIST are first met for iCR or iPR (whichever is first recorded) until the first date progression criteria according to iRECIST are met (see Section 7.8.6 for details).

Patients alive with no progression will be censored following the same censoring rules as for PFS (see Section 7.8.6). DDC can only be determined in patients with disease control as defined above. DDC according to RECIST/iRECIST is measured from the start of study treatment until the first date that PD is objectively documented according to RECIST/iRECIST (see Section 7.8.6 for details); alternatively censoring is applied according to the rules for PFS.

#### **7.8.6 Progression-free survival (PFS) and overall survival (OS)**

According to RECIST, PFS is defined as the period from the first dose of study drug until PD or death from any cause (whatever occurs first).

PFS is defined as the period from the first dose of study drug until the first time one of following events occurs

- Progression criteria according to iRECIST/RECIST met

- Start of non-trial systemic anti-cancer treatment (which is regarded as progression according to the protocol).
- death from any cause [REDACTED] after last post-baseline CT assessment [REDACTED] after first dose of study drug, if no post-baseline CT assessment is available.

Non-trial systemic anti-cancer treatment is defined as concomitant or post-study treatment/medication that is classified as chemotherapy in the eCRF. Mitotane therapy is not considered as non-trial system anti-cancer treatment.

According to RECIST the progression criteria is met at the first date of post-baseline CT assessment with PD documented as response, if not more than one scheduled CT assessment is missing or not evaluable before this CT assessment and the previous CT assessment was performed within [REDACTED] to this CT assessment.

According to iRECIST the progression criteria is met at the date of CT assessment with response documented as iUPD for that the next CT assessment documents iCPD as response (without any intervening assessments with other outcome), i.e. PD is confirmed, and if not more than one scheduled CT assessment is missing or not evaluable before the CT assessment with iUPD documented and the previous CT assessment was performed within [REDACTED] to CT assessment with IUPD documented. If progression is not confirmed and there is no subsequent CT assessment with iSD, iPR or iCR as response then the iUPD date will still be used as date of progression met in the following scenarios:

- no further response assessments are done or
- the next timepoint responses are all iUPD, and iCPD never occurs.

Non-trial systemic anti-cancer treatment is defined as concomitant or post-study treatment medication that is classified as chemotherapy in the eCRF. Mitotane therapy is not considered as non-trial system anti-cancer treatment.

Patients without an event as defined above will be censored based on the rules in Table 3.

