### 3.2.2 Secondary endpoints

The key secondary objectives of the trial are:

- Percentage of patients with shown immunogenicity

[figure not shown]
to EO2316, EO2317, EO2318, and UCP2 that compose EO2401

[figure not shown]
Cross reactivities with the human TAAs IL13Ra2, FOXM1, and BIRC5/survivin will also be evaluated

[figure not shown]
The other secondary endpoints of the trial are:

- ORR, time to response, and DOR as described by RECIST 1.1 [36] and iRECIST criteria [37]; see [Section 12.1](#) for an outline of response criteria.
- PFS as described by RECIST 1.1 and iRECIST criteria, defined as the time interval from the date of first study treatment administration to the date of progression (by RECIST 1.1 or iRECIST criteria) or death due to any cause, whichever is earlier. Patients without progression or death are to be censored at the time of the last tumor assessment.
- OS defined as the time interval from the date of first study treatment administration to the date of death due to any cause. Patients alive will be censored at the date of the last documented follow-up.
- In addition, in the randomized extension of Cohort 2A safety and tolerability of EO2401/nivolumab will be assessed versus internal concurrent controls (groups of patients treated with EO2401 monotherapy and nivolumab monotherapy, respectively), by incidences of adverse events (AEs), treatment-emergent AEs (TEAEs), serious AEs (SAEs); AEs will be analyzed irrespective of relationship, and as related events.

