### 6.9.3 Prohibited medications and other therapies

The use of systemic corticosteroids and other immunosuppressants should be avoided because of their potential interference with the pharmacodynamics activity of the study treatment. However, in some cases, systemic corticosteroids cannot be avoided; guidance

regarding steroid use for patients participating in the trial is therefore outlined in [Section 6.9.2](#).

The use of live or attenuated vaccine therapy for prevention of infectious diseases during trial participation should be avoided if possible. However, if such vaccinations would be considered as important for the normal care of the patient, the treating physician should discuss the situation with the Medical Monitor of the Sponsor and an adequate solution regarding timing should be found.

Patient should be discouraged from taking medications, including herbal remedies, with immunostimulatory properties, or known to potentially interfere with major organ function, during trial participation. If needed, any such possible therapy should be discussed between the treating physician and the Medical Monitor of the Sponsor.

During trial participation patients should not receive any other anti-cancer treatment than the specific trial treatment (EO2401 in combination with nivolumab) and treatments outlined in [Section 6.9.2](#).

If any other anti-cancer treatment, or procedure, would be considered for start in an individual patient, it is the duty of the Investigator to discuss the consideration with the Medical Monitor of the Sponsor for a decision on how to handle continued trial specific treatment and trial participation.

In general, if necessary due to e.g. patient symptoms, local therapies will be promoted; depending on localization of the treatment versus localization of measurable lesions, a decision might be necessary to consider censoring the patient for progression related endpoints at the time of start of the therapy if there would be no measurable lesion left outside of the location of the local treatment (or assessing the patient as having progressive disease if relevant criteria would be fulfilled).

Start of non-trial systemic anti-cancer treatments would lead to censoring of the patient for progression related endpoints at the time of start of the therapy; or assessment of the patient as having progressive disease if relevant criteria would be fulfilled.

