**Table 3 Censoring rules for PFS**

Situation	Date of Event or Censoring
No CT assessment at baseline	Date of first study treatment administration
No progression nor death nor non-trial systemic anti-cancer treatment documented	Date of last post-baseline CT assessment
Death more than [REDACTED] after last post-baseline CT assessment	Date of last post-baseline CT assessment
Death more than [REDACTED] after first study treatment and without post-baseline CT assessment	Date of first study treatment administration
Progression criteria met after $\geq 2$ consecutive schedule missing CT assessments	Date of last post-baseline CT assessment before missing CT assessment
Progression criteria met [REDACTED] after previous CT assessment	Date of previous CT assessment

OS is defined as the period from the first dose of study drug until death due to any cause.

Patients alive at their last visit will be censored at the last visit date.

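### SAP 7.8.6 counts the start of new systemic therapy as a PFS event and attributes this to the protocol, but protocol 6.9.3 censors the patient at that point

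*SAP*

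**What the plan says.** SAP 7.8.6 gives two definitions of PFS. The opening RECIST sentence runs from first dose "until PD or death from any cause (whatever occurs first". The list that follows has three kinds of event: progression criteria met, death within a (redacted) interval, and "Start of non-trial systemic anti-cancer treatment (which is regarded as progression according to the protocol". In Table 3, the row for patients without an event applies only where there is "No progression nor death nor non-trial systemic anti-cancer treatment documented". No row censors a patient at the start of new therapy.

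Protocol 6.9.3 says that starting non-trial systemic anti-cancer treatment "would lead to censoring of the patient for progression related endpoints at the time of start of the therapy"; the alternative it allows is "or assessment of the patient as having progressive disease if relevant criteria would be fulfilled". Protocol 3.2.2 defines PFS as the time to "the date of progression (by RECIST 1.1 or iRECIST criteria) or death due to any cause, whichever is earlier", and adds: "Patients without progression or death are to be censored at the time of the last tumor assessment".

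SAP 7.8.5 ends DOR and DDC at documented progression, refers to 7.8.6 for the details, and otherwise borrows the PFS censoring rules.

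**The concern.** The SAP cites the protocol for a rule that the protocol does not contain. A reader of the study report would be told that the protocol requires switches to count as progression, when 6.9.3 directs censoring.

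The rule feeds the secondary PFS curves, the medians, the 6-, 12-, 18- and 24-month estimates and any Cox models in SAP 7.8.7. SAP 4.2 gives cohorts of 2 to 26 patients, so one reclassified patient can move an estimate visibly. DOR and DDC are affected through 7.8.5. A responder who switches without progression has no objectively documented progression, yet 7.8.6 treats the switch as an event and Table 3 gives no censoring row for that patient. Two programmers could derive different end dates.

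**Working it through.** **Text comparison.** How each passage treats a patient who starts new systemic therapy without having met progression criteria:

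- SAP 7.8.6, event list: event at therapy start.
- SAP 7.8.6, opening RECIST sentence: no event, because only progression or death counts.
- Protocol 6.9.3: censored at therapy start.
- Protocol 3.2.2: no event at therapy start. A patient with no progression or death is censored at the last tumor assessment.

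The exception in 6.9.3 does not rescue the SAP. Patients who meet progression criteria are already caught by the separate progression bullet in 7.8.6. The new-therapy bullet therefore acts only on patients who do not meet them, and these are the patients whom 6.9.3 censors.

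**Illustration of size.** The plan has no figure to reproduce. The CT weeks (9, 17, 25) come from SAP 7.8.1 and the cohort sizes from SAP 4.2. The event counts and switch times are assumptions.

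Base case: n = 13, progression in 6 patients at week 9 and 2 at week 17, one switch at week 12 without progression, and 4 patients event-free beyond 6 months. The Kaplan-Meier estimate multiplies (1 − events / number at risk) over the event times.

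- After week 9, under both rules: 7/13.
- SAP rule: 7/13 × 6/7 × 4/6 = 4/13 = 30.8%. The curve falls to 6/13 = 46.2% at week 12, so median PFS is 12 weeks.
- Protocol 6.9.3: 7/13 × 4/6 = 35.9%. The median is 17 weeks. Censoring at the week-9 CT instead of at week 12 gives the same result.
- Primary-endpoint rule (SAP 4.4.1, followed whatever the later treatment), if the switcher stays progression-free to 6 months: 5/13 = 38.5%.

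Varying the assumptions, 6-month PFS is:

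| Assumed case | Event (SAP) | Censored (6.9.3) | Gap, points |
|---|---|---|---|
| n = 13, one switch at week 4 | 4/13 = 30.8% | 6/12 × 4/6 = 33.3% | 2.6 |
| n = 13, one switch at week 12 | 4/13 = 30.8% | 7/13 × 4/6 = 35.9% | 5.1 |
| n = 13, one switch at week 20 | 4/13 = 30.8% | 5/13 = 38.5% | 7.7 |
| n = 13, two switches at week 12 | 3/13 = 23.1% | 7/13 × 3/5 = 32.3% | 9.2 |
| n = 13, three switches at week 12 | 2/13 = 15.4% | 7/13 × 2/4 = 26.9% | 11.5 |
| n = 26, one switch at week 12 | 9/26 = 34.6% | 14/26 × 9/13 = 37.3% | 2.7 |
| n = 4, one switch at week 12 | 1/4 = 25.0% | 2/4 = 50.0% | 25.0 |

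The n = 26 row doubles the progressions (12 and 4). The n = 4 row has 2 progressions at week 9 and one patient event-free.

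**Time to objective response.** SAP 7.8.4 censors non-responders at the PFS event time. For a switcher that is therapy start under the SAP rule, and it is also therapy start if 6.9.3 is followed. The effect on this endpoint is negligible.

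**The case against.** Several counter-arguments have force.

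- **The event rule is a legitimate, cautious choice.** Patients who switch without formal progression may be deteriorating, so censoring them can be informative, and counting them as events does not flatter the treatment. This supports keeping the rule as a sensitivity analysis. It does not make the attribution to the protocol true.
- **SAP 5.3 (changes from planned analyses) is redacted and may declare a change.** It may, but a declared change could not stand beside a statement that the protocol already says so.
- **The data review meeting deals with this.** Under SAP 7.8.1 that meeting decides whether CTs after further anti-cancer treatment are used, and confirms which treatments qualify. It does not turn an event into censoring.
- **Few patients may be affected.** Under iRECIST, 7.8.6 already dates an event at an unconfirmed progression with no further assessment, which narrows the group. Nothing in the documents shows that anyone switched without progression.
- **The protocol is not fully consistent.** This stands. Read alone, 3.2.2 has no censoring for new therapy and uses the last tumor assessment, while 6.9.3 censors at therapy start. For a patient who switches at week 12 without progression and dies at week 40, 6.9.3 censors and 3.2.2 counts the death.

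A reader might also infer that Table 3 is wrong wherever it censors late deaths (for example "Death more than [REDACTED] after last post-baseline CT assessment") or progression after missed scans or a long gap between CTs. Those rows do depart from the literal wording of 3.2.2. They are nevertheless a recognised analysis choice, their windows are partly redacted, and SAP 5.3 may declare them. The documents do not support calling them errors.

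**Conclusion.** The attribution in SAP 7.8.6 is wrong as written, and the rule attached to it conflicts with protocol 6.9.3 and with the SAP's own opening RECIST definition. It should be corrected.

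The rule lowers secondary PFS relative to protocol censoring. In the assumed 13-patient example, one switch costs 2.6 to 7.7 points at 6 months, depending on its timing (5.1 points at week 12). The gap grows with more switches and in smaller cohorts. These figures show direction and sensitivity only, because the event counts and switch times are invented and the number of affected patients is unknown. The treatment of new therapy in DOR and DDC is ambiguous.

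A reader might infer that the 6-month primary endpoint is compromised. The documents do not show this. SAP 4.4.1 follows patients whatever they receive later, and the visible non-survivor categories in 7.8.2 are death, progressive disease and loss to follow-up, with none for new therapy. Much of 7.8.2 is redacted. What can be said is that, on the visible text, one Cohort 2A-I patient could be progression-free in the primary table and a PFS event in the 6-month estimate of 7.8.7.

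**What to change.** 1. In SAP 7.8.6, delete the new-therapy event bullet and its attribution to the protocol.
2. Add a Table 3 row that censors at the start of non-trial systemic anti-cancer therapy when progression criteria have not been met, as protocol 6.9.3 directs. Apply it to PFS, DOR and DDC.
3. State that this row takes precedence over any later progression or death in the main analysis, so that a patient who switches and then dies has one defined outcome.
4. Reconcile protocol 6.9.3 with 3.2.2, both on whether to censor for new therapy and on the date (therapy start or last tumor assessment).
5. Keep the present SAP event rule as a sensitivity analysis.
6. At most, for the late-death and late-progression rows of Table 3: declare them as a departure from 3.2.2 and add a sensitivity analysis that counts those deaths and progressions as events.

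The cost is SAP wording, one table row, re-derived PFS, DOR and DDC dates, the sensitivity runs, and a short clarification reconciling the two protocol sections. It needs no new data and no change to trial conduct.

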#### ***1.1.4 Treatment of malignant pheochromocytoma/paraganglioma***

The therapeutic strategy of metastatic MPP aims to control excessive catecholamine secretion and tumor burden, but no curative treatment is achievable. Treatment choices include a wait and see policy, locoregional therapies, systemic chemotherapy, and radiopharmaceutical agents [6].

In the absence of any randomized studies and demonstrated impact on survival, the patients' quality of life should always be considered. Indeed, due to the indolent course of subgroups of patients, a wait and see policy coupled with a watchful follow-up can be considered as an option in asymptomatic patients with a low tumor burden.

An antineoplastic treatment is often recommended in case of rapid progression and/or symptom onset. In the absence of tumor progression, surgery of the primary tumor or metastases can reduce hormone secretion and may prevent complications related to a critical anatomical location and improve the efficacy of subsequent therapies [6]. Metastatic disease palliation may also benefit from local therapy with embolization and or radiofrequency ablation.

Radionuclide therapy is an effective treatment and I-MIBG is the most frequently used. Approximately 50% of patients are eligible for I-MIBG therapy based on the uptake on diagnostic scans. Several studies have been published on the efficacy of I-MIBG treatment [6]; objective responses were observed in 22–47% of patients, mainly in patients with soft tissue metastases. I-MIBG therapy might be considered as a first-line approach in patients with a good uptake of I-MIBG and unresectable, progressive MPP or patients with symptoms (not amenable to locoregional control), or patients with a high tumor burden with a low number of bone metastases.

Cyclophosphamide- and dacarbazine-based regimens combined with vincristine (CVD) or doxorubicin (CVDD or CDD) are the best studied chemotherapy regimens [6]. In one of the larger published studies (n = 52 patients), 40% of patients treated with CVD, CDD, or CVDD experienced clinical benefits, including a reduction in tumor size in 25% of cases [16]. Systemic chemotherapy is debated as a first-line therapy in patients with a low uptake of I-MIBG and unresectable, rapidly progressive MPP, or patients with high tumor burden or with a high number of bone metastases.

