Most recently, at ESMO 2021, the first international randomized study in malignant progressive pheochromocytoma and paragangliomas (FIRSTMAPPP) was presented [68]. Patients with progressive MPP were randomized 1:1 for sunitinib therapy or placebo. The primary endpoint was progression-free survival (PFS) at 12 months. On the basis of a two-step Simon model (alpha 10%, power 90%), the investigators aimed for 74 patients, assuming a PFS improvement at 12 months from 20 to 40%. Eleven or more patients out of 37 with no progression at 12 months were expected to conclude that sunitinib is effective. The placebo group served as an internal control to validate the hypothesis of the Simon design with a 12-month PFS equal to 20%.

A total of 78 patients were enrolled (39 randomized in each arm) including adrenal/paraganglioma primaries, each 50%, and 60% patients with prior therapy. The primary endpoint was met: PFS at 12 months was 35.9% with sunitinib versus 18.9% with

placebo. Median PFS was 8.9 months (95% CI: 5.5-12.7) versus 3.6 months (95% CI: 3.1-6.1). The investigators conclusion was that sunitinib becomes the first-line option in patients with progressive MPP.

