### 7.8.1 General aspects of response related endpoints

The response assessments during the treatment period follow the scheduled CTs post

baseline, planned for the visits at study weeks 9, 17, 25 (+/- 4 days), and from Week 25 onwards every 8 weeks (+/- 4 days). Unscheduled CT assessments as well as planned CT scans performed on the day of study drug administration [REDACTED]

[REDACTED] are also possible. For patients who are discontinuing all study treatment without having had confirmation of progressive disease (PD) according to iRECIST criteria [Seymour et al], CT assessments are scheduled every 8 weeks (+/- 4 days) after the latest performed CT assessment during the time period they received study treatment.

If not otherwise stated, all response assessments collected by investigator (local assessments) during the study will be considered, regardless of whether they come from scheduled or unscheduled assessments and if they were assessed during or after study treatment.

In principle, any further anti-cancer treatment during the study, i.e. prior to the individual study treatment termination, is prohibited. If nevertheless a patient is treated with further anti-cancer treatment during the study, the inclusion of CT assessments after introduction of further anti-cancer treatment in the derivation of response related and time to event endpoints will be agreed on and documented during the DRM. Also, the non-trial systemic anti-cancer treatments defined in Section 7.8.5 and 7.8.6 will be confirmed during the DRM.

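### SAP 7.8.6 counts only medication classified as chemotherapy as a switch of systemic anti-cancer therapy, which is narrower than Protocol 6.9.3 and makes secondary PFS inconsistent between patients who switch

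*SAP*

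**What the plan says.** - **Definition.** SAP 7.8.6 says, in two places: "Non-trial systemic anti-cancer treatment is defined as concomitant or post-study treatment/medication that is classified as chemotherapy in the eCRF". One agent is excepted: "Mitotane therapy is not considered as non-trial system anti-cancer treatment".
- **Role in PFS.** SAP 7.8.6 lists as a PFS event: "Start of non-trial systemic anti-cancer treatment (which is regarded as progression according to the protocol").
- **Protocol rule.** Protocol 6.9.3 says: "Start of non-trial systemic anti-cancer treatments would lead to censoring of the patient for progression related endpoints". The censoring is at the start of that therapy, or the patient is assessed as progressed if the criteria are fulfilled. No drug class is named.
- **Scans that count.** SAP 7.8.1 uses local assessments made during or after study treatment. Table 3 censors a patient with no recognised event at the last post-baseline CT.
- **Data review meeting (DRM).** SAP 7.8.1 makes two provisions. If further anti-cancer treatment of any class starts before study treatment ends, the meeting decides whether later scans enter the endpoints. Separately, "the non-trial systemic anti-cancer treatments defined in Section 7.8.5 and 7.8.6 will be confirmed during the DRM".
- **Possible next therapies.** Protocol 1.1.4 reports the conclusion that "sunitinib becomes the first-line option in patients with progressive MPP" and says of MPP: "Radionuclide therapy is an effective treatment". Protocol 1.2 describes checkpoint inhibitors under test in ACC and MPP.

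**The concern.** The protocol does not use chemotherapy as a word for all systemic therapy. Section 1.1.4 lists systemic chemotherapy and radiopharmaceuticals as separate choices, and Section 2.1 presents sunitinib as an alternative to chemotherapy. Followed as written, the SAP therefore handles two otherwise identical patients differently. One who starts chemotherapy after stopping study treatment has a PFS event that day. One who starts sunitinib, radionuclide therapy or another checkpoint inhibitor carries on, and scans on the new drug extend PFS.

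At stake are the secondary PFS estimates in small cohorts. The mix of next therapies may differ between ACC and MPP, so the difference in handling could also enter the ACC versus MPP covariate in the Cox model of SAP 7.8.7.

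**Working it through.** The plan gives no figure for this point, so there is none to reproduce. The check is a comparison of the texts, followed by an illustration of size.

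**1. The path of one patient.** The patient stops study treatment without recognised progression and starts a systemic agent outside the chemotherapy category.
- CTs continue every 8 weeks (SAP 7.8.1), and scans after study treatment count.
- The new agent does not meet the 7.8.6 definition, so there is no event.
- Table 3 censors at the last CT, including one taken on the new agent; a later progression is dated on the new agent.
- Under iRECIST, an unconfirmed progression stops counting if a later CT shows iSD, iPR or iCR (SAP 7.8.6). Disease control on the new agent could therefore also cancel an earlier unconfirmed progression.

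Under Protocol 6.9.3 the same patient would be censored at the switch, or assessed as progressed if the criteria were met.

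**2. Whether the DRM closes the gap.** The case-by-case ruling on scans covers therapy started before study treatment ends. This patient switches afterwards. The other provision confirms treatments as defined in 7.8.5 and 7.8.6. Section 7.8.5 contains no such definition, and 7.8.6 contains only the chemotherapy one. No criteria for widening it are given.

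**3. Size under the SAP's event rule.** Suppose k switchers would otherwise be event-free past a landmark, with no other censoring before it. Counting each switch as an event lowers the landmark PFS estimate by k/n. Cohort sizes are from SAP 4.2; k is assumed.

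| Cohort | n | k=1 | k=2 | k=3 |
|---|---|---|---|---|
| 3B | 5 | 20.0 points | 40.0 | 60.0 |
| 3A, 2A-I | 13 | 7.7 | 15.4 | 23.1 |
| 2A non-randomized | 26 | 3.8 | 7.7 | 11.5 |

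With k = 0 nothing changes.

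**4. Direction depends on the rule.** Assumed example with n=5: events at months 2, 4, 9 and 12, and one switch at month 6. In every version S(2) = 4/5 = 0.8 and S(4) = 0.8 × 3/4 = 0.6.
- Switch as event: S(6) = 0.6 × 2/3 = 0.4, median 6.
- Switch censored: two remain at risk at month 9, S(9) = 0.6 × 1/2 = 0.3, median 9.
- Switch ignored, progression at 14.9: S(9) = 0.6 × 2/3 = 0.4, median 9.
- Switch ignored, progression at 8: S(8) = 0.6 × 2/3 = 0.4, median 8.

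Ignoring the switch lengthens the median against the event rule (8 or 9 versus 6). Against the protocol's censoring rule it leaves the median the same or shortens it (9 or 8 versus 9).

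**5. Linked endpoints.** SAP 7.8.5 ends DOR and DDC at documented progression and otherwise borrows the PFS censoring rules. The no-event row of Table 3 requires that no non-trial systemic treatment was documented, and no row says what happens to DOR or DDC when one was. Even a chemotherapy switch does not clearly end them.

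**The case against.** The strongest reply is that only a mismatch of wording is established. The eCRF categories are not in the documents, and the chemotherapy category may be wider than cytotoxic drugs. SAP 5.3, on changes to planned analyses, cannot be read, so a stated reason cannot be excluded. Where radionuclide therapy is recorded is also unknown: SAP 7.7 summarises radiotherapies with procedures, while exclusion criterion 4 in Protocol 5.2 names radionuclide therapy and radiotherapy separately. This stands against any claim that switches are certainly missed. It does not rescue the definition, which rests on a category the plan does not explain. The mitotane exception does not point to a wide category either, because Protocol 1.2 describes mitotane as cytotoxic.

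The DRM safeguard also stands in part. It confines the gap to therapy started after study treatment ends and before recognised progression. The Cox model is fitted only if events suffice, and Protocol 9.2 treats tests in the non-randomized cohorts as exploratory.

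A reader might infer more than the documents support:
- **That all 18 MPP patients (13 in 3A, 5 in 3B) are affected.** Only those who switch in that window are; 18 is the upper limit.
- **That a patient is credited with about 15 months instead of 6.** That adds an assumed 6 months on study to the 8.9-month sunitinib median in Protocol 1.1.4 (6 + 8.9 = 14.9). The 8.9 comes from another trial's randomised patients, and under the protocol's rule the 6 would be a censored time.
- **That the bias favours study treatment under either rule.** Step 4 shows this is clear only under the event rule.
- **That only EO2401/nivolumab gains.** The same definition applies to the monotherapy cohorts.

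**Conclusion.** The point holds for secondary PFS. The SAP's definition is narrower than the protocol's rule and, followed literally, treats switchers differently by drug class. Under the SAP's event rule the resulting PFS is too favourable; under the protocol's censoring rule the direction is not fixed. The shift per unrecognised switcher who stays event-free past a landmark is 20 points at n=5, 7.7 at n=13 and 3.8 at n=26. This assumes the switch would count as an event, no other censoring before the landmark, and an eCRF category that excludes the agent concerned. The number of such patients is not given and may be zero.

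A reader might extend this to the primary result. The documents do not support that: SAP 4.4.1 and Protocol 3.2.1 follow patients for the 6-month rate whatever other regimens they receive. OS is counted to death and is also unaffected.

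**What to change.** 1. Replace both definition sentences in SAP 7.8.6 with one covering every class, for example: *any systemic anti-cancer therapy other than study drug (cytotoxic, targeted, immune, radionuclide or investigational) started after Day 1, identified from both the medication and the procedure pages of the eCRF; mitotane is excepted.*
2. Reconcile the SAP's event rule, which it attributes to the protocol, with the censoring rule in Protocol 6.9.3. Name one as the main analysis and run the other as a sensitivity analysis.
3. Add a row to Table 3, or a sentence in 7.8.4 and 7.8.5, saying how a switch is handled for DOR, DDC and time-to-OR. Changing the definition alone does not repair these.
4. State the DRM criteria before data review and correct the reference to a definition in 7.8.5.

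The cost is SAP wording and a coding review. Protocol 7.5.2 and 7.5.3 already collect further anti-cancer treatments, so no new data are needed. PFS may become slightly less favourable.
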